14.7 Definition, Documentation and Reporting of Adverse Events specific for EU sites

14.7.1 Definitions

Adverse Events (AE)

An adverse event is any untoward medical occurrence, unintended disease or injury or any untoward clinical signs, including an abnormal laboratory finding, in subjects, users or other persons, in the context of a clinical investigation, whether it is considered to be device related or not.

Serious Adverse Event (SAE):

Any adverse event that led to any of the following:

- Death
- Serious deterioration in the health of the subject, that resulted in any of the following:
 - life-threatening illness or injury
 - permanent impairment of a body structure or a body function
 - hospitalization or prolongation of patient hospitalization
 - medical or surgical intervention to prevent life-threatening illness or injury or permanent impairment to a body structure or a body function
 - chronic disease
- fetal distress, fetal death or a congenital physical or mental impairment or birth defect

Adverse Device Effect (ADE)

Adverse event related to the use of an investigational medical device. This includes any adverse event resulting from insufficiencies or inadequacies in the instructions for use, the deployment, the implantation, the installation, the operation, or any malfunction of the investigational medical device. This includes any event that is a result of a use error or intentional misuse.

Serious Adverse Device Effect (SADE)

A SADE is one that has resulted in any of the consequences characteristic of a serious adverse event.

Unanticipated Serious Adverse Device Effect (USADE)

A USADE which by its nature, incidence, severity or outcome has not been identified in the current Risk Management section of the Investigator's Brochure (IB) and IFU.

Any serious adverse effect on health or safety or any life-threatening problem or death caused by, or associated with the Cordella PA Sensor System, that was not previously identified in nature, severity, or degree of incidence in the CIP, IB or IFU or any other unanticipated serious problem associated with the study device that relates to the rights, safety, or welfare of subjects.

An unanticipated event is one where the nature or intensity is not consistent with the information in the current Risk Management section of the CIP, IB and IFU.

Furthermore, reports which add significant information on specificity or severity of a known, already documented adverse effect constitute unanticipated events. For example, an event more specific or more severe than described in the IB would be considered 'unexpected'.

14.7.2 Causality Assessment

The relationship between the use of the medical device (including the medical - surgical procedure) and the occurrence of each adverse event shall be assessed and categorized as follows:

- **Not related**

Relationship to the device, comparator or procedures can be excluded when:

- the event has no temporal relationship with the use of the investigational device, or the procedures related to application of the investigational device;
- the serious adverse event does not follow a known response pattern to the medical device (if the response pattern is previously known) and is biologically implausible
- the discontinuation of medical device application or the reduction of the level of activation/exposure - when clinically feasible - and reintroduction of its use (or increase of the level of activation/exposure), do not impact on the serious adverse event;
- the event involves a body-site or an organ that cannot be affected by the device or procedure;
- the serious adverse event can be attributed to another cause (e.g. an underlying or concurrent illness/ clinical condition, an effect of another device, drug, treatment or other risk factors);
- the event does not depend on a false result given by the investigational device used for diagnosis, when applicable;

In order to establish the non-relatedness, not all the criteria listed above might be met at the same time, depending on the type of device/procedures and the serious adverse event.

- **Possible**

The relationship with the use of the investigational device or comparator, or the relationship with procedures, is weak but cannot be ruled out completely. Alternative causes are also possible (e.g. an underlying or concurrent illness/ clinical condition or/and an effect of another device, drug or treatment). Cases where relatedness cannot be assessed, or no information has been obtained should also be classified as possible.

- **Probably related**

The relationship with the use of the investigational device or comparator, or the relationship with procedures, seems relevant and/or the event cannot be reasonably explained by another cause.

- **Causal Relationship**

the serious adverse event is associated with the investigational device, comparator or with procedures beyond reasonable doubt when:

- the event is a known side effect of the product category the device belongs to or of similar devices and procedures;
- the event has a temporal relationship with investigational device use/application or procedures;
- the event involves a body-site or organ that
 - the investigational device or procedures are applied to;
 - the investigational device or procedures have an effect on;
- the serious adverse event follows a known response pattern to the medical device (if the response pattern is previously known);
- the discontinuation of medical device application (or reduction of the level of activation/exposure) and reintroduction of its use (or increase of the level of activation/exposure), impact on the serious adverse event (when clinically feasible);
- other possible causes (e.g. an underlying or concurrent illness/ clinical condition or/and an effect of another device, drug or treatment) have been adequately ruled out;
- harm to the subject is due to error in use;
- the event depends on a false result given by the investigational device used for diagnosis¹⁰, when applicable;

14.7.3 Safety Reporting

Regulations

Safety reporting will be performed in line with the requirements of the Regulation (EU) 2017/745 –Medical Device Regulation (MDR) Article 80(2) and MDCG 2020-10-1.

The sponsor will report, without delay to all Member States in which the clinical investigation is being conducted, all of the following (reportable events):

- a) any serious adverse event that has a causal relationship with the investigational device, the comparator or the investigation procedure or where such causal relationship is reasonably possible;
- b) any device deficiency that might have led to a serious adverse event if appropriate action had not been taken, intervention had not occurred, or circumstances had been less fortunate;
- c) any new findings in relation to any event referred to in points a) and b)

All causality assessments will be made as described in the section 9.2.2 of the CIP. Only causality level 1 (i.e. "not related") is excluded from reporting. If either the sponsor or the investigator has assigned a higher causality level than "not related", the event should be reported.

Safety reporting-Investigator:

As indicated in the section 9 of the CIP, the investigator must submit to sponsor (or designee) any UADEs and SAEs occurring during the study within 24 hours after being notified of the event and provide additional information, if required by Endotronix. In addition, any new finding regarding such events must be reported to the sponsor within the same time window (24 hours).

Germany: The reporting timelines for the investigator or principal investigator are in accordance with the requirements of Section 63 of the German Medical Device Law Implementation Act (MPDG).

For further information regarding the safety reporting by investigators please refer to the sections 9 and 11.3.1 of the CIP.

Reporting method:

A template for the Summary Reporting Form will be used for the safety reporting (please refer to the Appendix of MDCG 2020-10-01)

Report to whom

Reportable events must be reported all at the same time to all national competent authorities where the clinical investigation is authorized to start or has commenced.

Reportable events occurring in the USA

Reportable events occurring in the USA will be reported to the NCA(s) of the participating EU member states.

- The NCA will start receiving the reportable events occurring in the USA as soon as the clinical investigation is authorized to start in the participating EU Member State
- Events occurring in the USA after the participating European sites have closed will continue to be reported

Country Specific reporting timelines requirements

Country / Authority	Specific requirement to be met	Process to meet this requirement

Ireland/ Belgium
	
For all reportable events which indicate an imminent risk of death, serious injury, or serious illness and that requires prompt remedial action for other patients/subjects, users or other persons or a new finding to it: Immediately, but not later than 2 calendar days after awareness by sponsor of a new reportable event or of new information in relation with an already reported event.
 
Any other reportable events or a new finding/update to it: Immediately, but not later than 7 calendar days following the date of awareness by the sponsor of the new reportable event or of new information in relation with an already reported event.
 
The safety reports will be sent to: Belgium: [contact] Ireland: mailto:[contact]
	
All reportable SAEs will be processed in 2- day timeline (for SAEs which indicates an imminent risk of death, serious injury, or serious illness) and 7- day timeline for all other SAEs

Country / Authority	Specific requirement to be met			Process to meet this requirement
Germany	
A causal relationship between the SAEs and the investigational medical device, a comparator device, diagnostic or therapeutic procedures performed as part of the clinical trial or other conditions of the trial conduct cannot be excluded
 
To be reported immediately
	Germany	German SAE Report Form to: [contact]	
All reportable SAEs will be processed in 2 day timeline (for SAEs which indicates an imminent risk of death, serious injury, or serious illness requiring immediate corrective action) and 7 day timeline for all other SAEs.
 
New findings regarding an event will be reported within the original ridge requirement for that event.

	
A causal relationship between the SAE and the investigational medical device, a comparator device, diagnostic or therapeutic procedures performed as part of the clinical trial or other conditions of the trial conduct can be excluded
 
To be reported quarterly
	All other countries where the clinical trial is performed	
-Summary table
 
-Clinical Investigation Summary Safety Reporting form
	
SAE summary evaluation and cumulative Clinical Investigation Summary Safety Reporting form will be sent on a quarterly basis on predefined intervals

	All SAEs	All countries where the clinical trial is performed	
-SAE summary evaluation
 
-Annex 3.1 complication rate
	

Further guidance as well as a link to the aforementioned reporting forms can be found under the following link:
https://www.bfarm.de/EN/Medical-devices/Applications-and-reports/SAE-report/_node.html

14.8 PROACTIVE-HF Site Survey (V1.0/ 09 Nov 2021)

ETX-HFS-PA-03 (PROACTIVE- HF) Site Survey

Site #: **Patient #:**

At Unblinding Date /___/___/___/
 Day Month Year

Month 1 after Unblinding /___/___/___/
 Day Month Year

Quarterly

Month _ after Unblinding /___/___/___/
 Day Month Year

Thank you for participating in this short survey which will take less than 10mins.

The following questions refer to your review of the PAP and vital signs of the trial subjects in the former Control Group.

Please read the following 5 questions and mark the answer that best applies to you. There are no right or wrong answers.

#	Question	Answers
1	For this patient, are you using PAP Guided Heart Failure Management as per study guidelines?	 Yes  No Reason _____
2	How often do you review PAP trends and vital signs in the Patient Management Portal?	 2 times per week as per protocol  2-4 times per week  Daily  once per week
3	How often do you use PAP trends to adapt medication treatment?	 on a regular basis  on somewhat regular basis  Rarely  Never
4	How do you discuss Treatment changes with the patient?	 via phone  during on-site visit  via messaging using PMP  Other _____
5	Do you feel that having a combination of PAP and peripheral vital sign values help you to better manage and treat the patient's condition?	 I strongly agree  I agree  I somewhat agree  I disagree  I strongly disagree

14.9 PROACTIVE-HF Subject Survey (V2.0/ 11 Feb 2022)

**ETX-HFS-PA-03 (PROACTIVE- HF)
Subject Survey**

Site #: **Patient #:**

Month 1 after Unblinding /___/___/___/
 Day Month Year

Quarterly

Month _ after Unblinding /___/___/___/
 Day Month Year

Thank you for participating in this short survey which will take less than 10mins.

The following questions refer to your daily Pulmonary Artery Pressure (PAP) measurements.

Please read the following 9 questions and mark the answer that best applies to you. There are no right or wrong answers.

#	Question	Answers
1	Do you understand what Pulmonary Artery Pressure (PAP) is and why it is important to measure/monitor this parameter on a frequent basis?	 Yes  No
2	In general, how would you describe ease of use of taking daily Pulmonary Artery Pressure (PAP) readings using the Cordella system?	 Poor  Fair  Good  Very Good  Excellent
3	How long does a reading session take for you?	 < 2 min  2- 5 min  >5 min
4	How confident are you in using the myCordella tablet in finding PAP trends?	 Extremely  Slightly  Moderately  Very
5	Do you take notice and monitor your PAP trends in the "My Info" section of the myCordella tablet?	 No, I leave that to my doctor/nurse  I know what my normal trend range is and would know if it was higher or lower than normal
6	How often do you check your Pulmonary Artery Pressure (PAP) trends in the "My Info" section of your myCordella tablet?	 Never  Not Often (1-2 times every few months)  Often (1-2 times per month)  Very Often (at least 1-2 times per week)
7	Do you make changes to your lifestyle based on the Pulmonary Artery Pressure (PAP) trends you see? Lifestyle changes would include changes to diet, exercise, and smoking cessation among others.	 No, I only make lifestyle changes at the direction of my doctor/nurse  I sometimes make lifestyle changes on my own  I regularly use my daily measurements to make lifestyle changes on my own
8	How often are you communicating with your physician/nurse about your PAP trends and related Heart Failure medication(s)?	 Never  Not Often (1-2 times every few months)  Often (1-2 times per month)  Very Often (at least 1-2 times per week)
9	Overall how would you rate the impact Pulmonary Artery Pressure (PAP) readings and resulting clinician care have had on your health?	 Poor  Fair  Good  Very Good  Excellent

2.1	17-Aug-2023	[name]	
Repeated the primary safety analysis on ITT additionally. The cutoff for 6 month analysis updated to 180 days from 183 days
 
Added an AE summary for 'Other serious adverse events (AE) CEC adjudicated'
 
Added separate analyses of HFH and all-cause mortality from CEC adjudication results
 
The compression population update to Cohort #1, Cohort #2 and #3 from Cohort #1 and Cohort #2
 
The secondary endpoint #3 update to Comparison of the number of HF Hospitalizations or Emergency Department/ Hospital Outpatient IV diuretic visits of Cohort #1 and Cohort #2 + #3 at 6 and 12 months post implant from Comparison of the number of HF Hospitalizations or Emergency Department/ Hospital Outpatient IV diuretic visits of Cohort #1 and Cohort #2 at 6 and 12 months post implant
 
The secondary endpoint #14 Change from baseline in PAP parameters collected via CorPASS will not be performed for Cohort #1 population

This document is confidential.

I confirm that I have reviewed this document and agree with the content.

Approvals		
Syneos Health Approval		
[name], Biostatistician I	[name]	<small>Electronically signed by: [name] Reason: I am the author Date: Aug 17, 2023 14:58 GMT+8</small>
Lead Biostatistician	Signature	Date (DD-Mmm-YYYY)
[name], Principal Stat Programmer	[name]	<small>Electronically signed by: [name] Reason: I am the approver Date: Aug 17, 2023 10:28 GMT+2</small>
Lead Statistical Programmer	Signature	Date (DD-Mmm-YYYY)
[name], Assoc Dir, Biostatistics	[name]	<small>Electronically signed by: [name] Reason: I am the reviewer Date: Aug 17, 2023 17:52 GMT+8</small>
Senior Reviewing Biostatistician	Signature	Date (DD-Mmm-YYYY)
Endotronix, Inc.		
[name], Vice President Clinical Operations	[name]	<small>Electronically signed by: [name] Reason: I am the approver Date: Aug 17, 2023 09:11 GMT+2</small>
Sponsor Contact	Signature	Date (DD-Mmm-YYYY)

This document is confidential.

Table of Contents

Revision History	2
Approvals	3
1. Purpose.....	11
1.1. Responsibilities	11
1.2. Timings of Analyses.....	11
2. Study Objectives.....	12
2.1. Study Objective	12
2.2. Brief Description	12
2.3. Subject Selection.....	15
2.3.1. Inclusion Criteria.....	15
2.3.2. Exclusion Criteria.....	15
2.4. Determination of Sample Size.....	16
2.4.1. Primary Efficacy Endpoint (at 6 months post- implant).....	16

DD	Device Deficiency
dPAP	Diastolic Pulmonary Artery Pressure
DSMB	Data Safety Monitoring Board
DSRC	Device/System Related Complication
ED	Emergency Department
ECG	Electrocardiogram
GDMT	Guideline Directed Medical Therapy
GFR	Glomerular Filtration Rate
HF	Heart Failure
HFH	Heart Failure Hospitalization
HFEF	Heart Failure Ejection Fraction
HFpEF	Heart Failure with Preserved Ejection Fraction
HFReEF	Heart Failure with Reduced Ejection Fraction
HR	Heart Rate
INR	International Normalized Ratio
ITT	Intent to Treat
IWRS	Interactive Web Response System
KCCQ	Kansas City Cardiomyopathy Questionnaire
lb	Pound
LVEDD	Left Ventricular End Diastolic Dimension
LVEF	Left Ventricular Ejection Fraction
MAR	Missing at Random
Max	Maximum
MedDRA	Medical Dictionary for Regulatory Activities
Min	Minimum
mITT	Modified Intent to Treat
MNAR	Missing not at Random
mPAP	Mean Pulmonary Artery Pressure
N/A	Not Applicable
NCS	Not Clinically Significant
NYHA	New York Heart Association

This document is confidential.

Abbreviation	Description
PT	Preferred Term
PAP	Pulmonary Artery Pressure
PCWP	Pulmonary Capillary Wedge Pressure
pH	Potential of Hydrogen
PMA	Premarket Approval
PMP	myCordella™ Patient Management Portal
PP	Per protocol
PTT	Partial Thromboplastin Time
QC	Quality Control
QTc	Corrected QT Interval
RAP	Right Atrial Pressure
RBC	Red Blood Cell
RHC	Right Heart Catheterization
RVP	Right Ventricular Pressure
SAE	Serious Adverse Event
SADE	Serious Adverse Device Effects
SAP	Statistical Analysis Plan
SD	Standard Deviation
SI	Standard International System of Units
SGOT	Serum Glutamic Oxaloacetic Transaminase
SGPT	Serum Glutamic Pyruvic Transaminase
SpO2	Peripheral capillary oxygen saturation
sPAP	Systolic Pulmonary Artery Pressure
SOC	System Organ Class
SOP	Standard Operating Procedure
TFL	Table, Figure and Listing
WHO	World Health Organization
UADE	Unanticipated Adverse Device Effect

This document is confidential.

1. Purpose

The purpose of this statistical analysis plan (SAP) is to ensure that the data listings, summary tables and figures which will be produced, and the statistical methodologies that will be used, are complete and appropriate to allow valid conclusions regarding the study objectives.

1.1. Responsibilities

Syneos Health will perform the statistical analyses and is responsible for the production and quality control of all tables, figures, and listings. Health Economic analysis will be covered in a separate SAP.

Assessment of protocol deviations as minor or major for the definition of the analysis sets remains with the Sponsor.

1.2. Timings of Analyses

Main analysis will be performed after all Cohort #2- Previously enrolled Treatment Arm subjects and Cohort #3- Newly enrolled subjects completed the Month 6(V5) study visit or discontinued earlier. This main analysis will include all endpoints and analyses described in the SAP as far as data allow. The cleaning process will be completed at this stage, saying that the main analysis will be based on clean and coded data. Protocol deviations will be assessed and analysis sets will be defined following Syneos Health SOP (Blind) Data Review and Definition of Analysis Sets (3911) prior to the cut-off date for database (soft) lock. At this stage it will be decided if the analysis based on the Per-protocol population will be performed. Analysis will be performed on all analysis sets deemed relevant for the analysis. Listings will include all data collected until the cut-off date, by visit summaries will include data until V5 (Month 6), summaries (e.g. medication, or adverse events) without visit information will include all data until the cut-off date.

Additionally, an analysis on safety data will be performed once, the first 50 subjects which have been implanted with the Cordella PA Sensor have completed V4, Month 3 and also when 100 subjects have completed V3, Month 1. These safety analyses may occur at the same time depending on the timing of study visits. Analysis will be done on as much as possible clean and coded safety data.

The follow-up (final) analysis is planned after all subjects have completed the final study visit (V9, Year 3) or terminated early from the study.

An independent Data Safety Monitoring Board (DSMB) will review descriptive summaries of accumulating safety and subject disposition data on regular basis. Further description of the DSMB analyses can be found in the DSMB Statistical Analysis Plan Version 3.1 dated 07-Feb-2022 [1] and the DSMB charter Version 4.0 dated 04-Mar-2022 [1]. The study team from Syneos Health Biostatistics will perform the analyses.

The cut-off time point for the safety analysis and first two DSMB meetings expected to be identical. Outputs described in the DSMB SAP will cover the safety and DSMB analysis.

This document is confidential.

2. Study Objectives

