5.1. General Methods

- Unless otherwise specified, summaries will be presented by cohort (cohort #2 vs cohort #3) and overall
- Continuous variables will be summarized using the number of observations (n), mean, standard deviation (SD), median, minimum, and maximum. Categorical variables will be summarized using number of observations (n), frequency and percentages of subjects.
- All relevant subject data will be included in listings. All subjects entered into the database will be included in subject data listings, except screen failures. A separate listing will present the screen failures along with the inclusion criteria they failed and/or exclusion criteria they met. All listings except 16.2.3.x will be repeated for Cohort #1 population.
- In case of multiple assessments at a given time point (planned, repeat, unscheduled) the planned visit will be used for the analysis. For the definition of the baseline value, the last available value (e.g. unscheduled) prior to implant of Cordella PA Sensor will be used.

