8.1. Primary safety endpoint

8.1.1. Main analysis

There are two primary safety endpoints:

- 1) Freedom from device/system related complication at 6 months. Freedom from device or system related complications at 6 months will be tested against the null rate of 90%. The endpoint will be assessed based on the AE CRF page with adverse event type = 'Device / System-Related Complication'
- 2) Freedom from pressure sensor failure at 6 months. Freedom from Pressure Sensor Failure at 6 months will be tested against the null rate of 95%. The endpoint will be assessed based on the AE CRF page with adverse event type = 'Pressure Sensor Failure'

Each of these will be assessed within among all subjects who underwent a device implant by estimating freedom from the event of interest at 6 months by the Kaplan-Meier method.

Definition of time to event (days):

In case of event, time to event = [(Date of event – date of Implant visit) + 1]

In case of no event, time to event = [(Date of last available date or date of day 180 [6 months] – date of Implant visit) + 1], this data will be censored.

The event free rate and respective 95% Cis based on KM method will be compared to the null rate.

For endpoint 1:

H0: rate of freedom from device/system related complication at 6 months \leq 90 %

H1: rate of freedom from device/system related complication at 6 months $>$ 90

For endpoint 2:

H0: rate of freedom from pressure sensor failure at 6 months \leq 95 %

H1: rate of freedom from pressure sensor failure at 6 months $>$ 95 %

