8.2. Secondary safety endpoints

- 1) Pressure sensor failure rate throughout the study
- 2) Frequency of serious adverse events throughout the study
- 3) Frequency of implant procedure and procedure related adverse events and serious adverse events

Both secondary endpoints will be evaluated based on the AEs information and covered by AEs outputs.

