8.3.4. Presentation

Tables will be presented as listed below.

- An overall summary of the number and percentage of subjects reporting AEs, serious AEs, study procedure related AEs, serious study procedure related AEs, AEs leading to withdrawal and AEs leading to death, DSRC, Unanticipated Adverse Device Effect (UADE), implant procedure related AEs, serious implant procedure related AEs, and subjects who died.
- Predefined AEs by category
- AEs, overall and by SOC and preferred term
- Serious AEs, overall and by SOC and preferred term
- Serious AEs, overall and by preferred term
- Serious AEs by Seriousness Criteria
- Serious predefined AEs by category

This document is confidential.

- Study procedure related AEs, overall and by SOC and preferred term
- Serious study procedure related AEs, overall and by SOC and preferred term
- Implant procedure related AEs, overall and by SOC and preferred term
- Serious implant procedure related AEs, overall and by SOC and preferred term
- Study procedure related AEs by procedure type
- AEs by maximum severity, overall and by SOC and preferred term
- AEs by maximum relationship to implant procedure, overall and by SOC and preferred term
- DSRC, overall and by SOC and preferred term
- DSRC by maximum severity, overall and by SOC and preferred term
- DSRC, by devices
- UADE, overall and by SOC and preferred term
- UADE by maximum severity, overall and by SOC and preferred term
- UADE, by devices
- Implant procedure related AEs, overall and by SOC and preferred term
- Predefined AEs by relationships to device and study procedure from CEC adjudication results
- AEs leading to study withdrawal, overall and by SOC and preferred term
- Device deficiency will be presented as described in Section [8.3.1.1](#)
- AEs, overall and by SOC and preferred term will be done for subjects with predefined AE category 'Pressure Sensor Failure'.
- anticipated AEs, overall and by SOC and preferred term
- anticipated AEs by maximum severity, overall and by SOC and preferred term
- anticipated AEs by maximum relationship to implant procedure, overall and by SOC and preferred term
- unanticipated AEs, overall and by SOC and preferred term
- unanticipated AEs by maximum severity, overall and by SOC and preferred term

This document is confidential.

- unanticipated AEs by maximum relationship to implant procedure, overall and by SOC and preferred term
- Other serious adverse events (AE) CEC adjudicated by system organ class and preferred term

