	14.3.1.1.8	Freedom from device/system related complication: Kaplan-Meier plot	mITT Population
	14.3.1.1.9	Freedom from device/system related complication: Kaplan-Meier plot, stratified by sex	mITT Population
	14.3.1.1.10	Freedom from device/system related complication: Kaplan-Meier plot, stratified by heart failure ejection fraction	mITT Population
	14.3.1.1.11.1	Freedom from device/system related complication : Kaplan-Meier plot	Per Protocol Population
	14.3.1.1.11.2	Freedom from device/system related complication : Kaplan-Meier plot	ITT Population
	14.3.1.1.12	Freedom from device/system related complication : Kaplan-Meier plot	Cohort #1 Population
	14.3.1.1.20	Freedom from device/system related complication from CEC adjudication results: Kaplan-Meier plot	mITT Population
	14.3.1.1.21	Freedom from device/system related complication from CEC adjudication results: Kaplan-Meier plot, stratified by sex	mITT Population
	14.3.1.1.22	Freedom from device/system related complication from CEC adjudication results: Kaplan-Meier plot, stratified by heart failure ejection fraction	mITT Population
	14.3.1.1.23.1	Freedom from device/system related complication from CEC adjudication results: Kaplan-Meier plot	Per Protocol Population
	14.3.1.1.23.2	Freedom from device/system related complication from CEC adjudication results: Kaplan-Meier plot	ITT Population
	14.3.1.1.24	Freedom from device/system related complication from CEC adjudication results: Kaplan-Meier plot	Cohort #1 Population
	14.3.1.2.8	Freedom from pressure sensor failure: Kaplan-Meier plot	mITT Population
	14.3.1.2.9	Freedom from pressure sensor failure: Kaplan-Meier plot, stratified by sex	mITT Population
	14.3.1.2.10	Freedom from pressure sensor failure: Kaplan-Meier plot, stratified by heart failure ejection fraction	mITT Population
	14.3.1.2.11.1	Freedom from pressure sensor failure: Kaplan-Meier plot	Per Protocol Population
	14.3.1.2.11.2	Freedom from pressure sensor failure: Kaplan-Meier plot	ITT Population
	14.3.1.2.12	Freedom from pressure sensor failure: Kaplan-Meier plot	Cohort #1 Population
	14.3.1.2.20	Freedom from pressure sensor failure from CEC adjudication results: Kaplan-Meier plot	mITT Population
	14.3.1.2.21	Freedom from pressure sensor failure from CEC adjudication results: Kaplan-Meier plot, stratified by sex	mITT Population

This document is confidential.

Header	Table Number	Name	Analysis Set

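### At the main analysis, AE, SAE and secondary sensor-failure summaries are crude percentages of subjects to the cut-off, shown by cohort, although Cohort #2 probably has about 2.4 times the follow-up of Cohort #3

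*SAP*

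**What the plan says.** Four parts of the SAP combine.

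- **Data window.** Section 1.2 ends by-visit summaries at V5 for the main analysis. For the rest, "summaries (e.g. medication, or adverse events) without visit information will include all data until the cut-off date".
- **Layout.** Section 5.1: "Unless otherwise specified, summaries will be presented by cohort (cohort #2 vs cohort #3) and overall".
- **Statistic.** Section 8.3.4 opens its list of tables with "An overall summary of the number and percentage of subjects reporting AEs, serious AEs, study procedure related AEs" and so on. Section 12.2.4.2 makes the number of subjects the default denominator for percentages. The table index (section 14, 14.3.1.3 to 14.3.1.31) lists no AE table per patient-year or for a fixed window.
- **Secondary safety endpoints.** Section 8.2 lists three, the first being "Pressure sensor failure rate throughout the study", and then says: "Both secondary endpoints will be evaluated based on the AEs information and covered by AEs outputs". No denominator is given for that rate, and the text says both where three are listed.

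The two primary safety endpoints are handled differently. Section 8.1.1 assesses device/system-related complications (DSRC) and sensor failure by "estimating freedom from the event of interest at 6 months by the Kaplan-Meier method", and the index of figures (section 15) includes "Freedom from pressure sensor failure: Kaplan-Meier plot".

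**The concern.** Cohort is nearly the same thing as calendar time of implant. Cohort #2 is the former treatment arm, and Cohort #3 was enrolled after the change to a single arm. The main analysis is triggered when the last Cohort #3 subjects reach Month 6, so the cut-off finds Cohort #2 with far more time at risk. A percentage of subjects with an event then mixes the event rate with the length of observation.

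Two readings suffer. The by-cohort columns are where a reader would judge whether subjects from before and after the amendment look alike enough to pool, and unequal follow-up can create a difference or hide a real one. The overall column is not a rate: it rises with a later cut-off, so it cannot be set beside figures from studies with a different follow-up. This is the analysis that Protocol 6.1 ties to the PMA submission. Section 6.1 of the SAP does not list follow-up duration among the disposition summaries, so a reader could not correct the percentages from the tables.

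**Working it through.** **1. The plan's own safety figures.** The documents give no follow-up or AE frequency by cohort. The nearest stated figures are the safety powers in SAP 2.4.3 (above 95% at N = 450, maintained at 406). An exact binomial test at one-sided 0.025 gives:

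- sensor failure, 98.4% against 95%: 98.5% power at 450 (success at 437 or more event-free) and 96.7% at 406 (395 or more);
- DSRC, 95% against 90%: 98.1% and 96.4%.

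These reproduce. The planning rates of 1.6% and 5% per 6 months are used below.

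**2. Follow-up by cohort.** Inputs: first implant Q4 2019 and last implant estimated for Q1 2023 (Protocol 6.3); single-arm design in protocol version 7.0 of 11 November 2021 (amendment history). Assumptions: mid-quarter dates, cut-off six months after the last implant, a clean switch in November 2021, even accrual. In months from 1 October 2019: first implant 1.5, switch 25.3, last implant 40.5, cut-off 46.5.

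- Cohort #2: 46.5 − 25.3 = 21.2 to 46.5 − 1.5 = 45.0; mean 33.1.
- Cohort #3: 6.0 to 46.5 − 25.3 = 21.2; mean 13.6.
- Ratio 33.1 / 13.6 = 2.4.

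For sensitivity, first implant ran from October 2019 to January 2020, the switch from November 2021 to about May 2022 and last implant from January to end of March 2023. Accrual was even, early-loaded or late-loaded, with or without a constant dropout hazard μ = −ln(0.90)/6 = 0.0176 per month (Protocol 6.1: about 10% by 6 months). Even accrual gives 2.4 to 2.95 without attrition and 2.0 to 2.5 with it. All shapes together give 1.6 to 3.4.

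**3. Crude percentages from identical hazards.** With constant hazard λ and follow-up uniform on (a, b), the expected percentage with an event is

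1 − [exp(−λa) − exp(−λb)] / [λ(b − a)].

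With attrition, replace λ by λ + μ and multiply the result by λ/(λ + μ). Example, sensor failure: λ = −ln(0.984)/6 = 0.00269 per month. Cohort #2: 1 − (0.9446 − 0.8861)/(0.00269 × 23.8) = 8.5%. Cohort #3: 1 − (0.9840 − 0.9446)/(0.00269 × 15.2) = 3.6%.

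| Event, same hazard in both cohorts | #2 vs #3, no attrition | #2 vs #3, with attrition |
|---|---|---|
| Sensor failure, 1.6% per 6 months | 8.5% vs 3.6% | 6.4% vs 3.2% |
| DSRC, 5% per 6 months | 24.5% vs 10.9% | 18.7% vs 9.6% |
| Common event, hazard 0.34 per 6 months | 83.5% vs 52.3% | 68.9% vs 47.0% |
| Rare event, 0.3% per 6 months | 1.6% vs 0.7% | 1.2% vs 0.6% |
| 2%, all in first 30 days | 2.0% vs 2.0% | not run |

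The common-event row borrows the planning HFH/death rate (SAP 2.4.1) as a first-event hazard, for illustration. Its gap is 31 points, or 22 with attrition. At the extreme ratios it is 66.5% vs 51.3% (15 points, ratio 1.6, with attrition) and 78.7% vs 38.5% (40 points, ratio 3.4, without). Sensor failure in those two cases is 5.8% vs 3.6% and 7.6% vs 2.3%. Measured over a common 6 months, every row shows no difference.

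**4. Final analysis.** SAP 1.2 places it after everyone reaches Year 3 or leaves. If data stop at Year 3 for all, potential follow-up is equal. If they run to that date under the protocol's 5-year limit, Cohort #2 has 51.2 to 75 months capped at 60, mean (8.8 × 55.6 + 15.0 × 60)/23.8 = 58.4. Cohort #3 has 36 to 51.2, mean 43.6. The ratio is then 1.3.

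**The case against.** The strongest reply is that nothing confirmatory rests on these tables. The sensor-failure and DSRC tests are Kaplan-Meier estimates at 6 months with censoring, compared with fixed goals. No formal test is planned for other safety data, and no safety comparison of Cohort #2 with Cohort #3 is specified. AE onset day is derived, all AEs are listed, disposition shows completion of Months 6 and 12, and all outputs are refreshed at the final analysis. All of this stands. It keeps the point at the level of a recommended improvement.

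Some stronger readings are tempting and should be resisted.

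- A reader might infer that sensor failure is analysed only as a crude percentage. It is not: only the secondary whole-study summary is exposed.
- A reader might infer that all three secondary safety endpoints are distorted. The third concerns procedure-related events, which fall largely around implant and are barely affected.
- A reader might infer that large differences will appear and will be nothing but time at risk. Rare events differ by about a point, and Protocol 3.3 reports no sensor failures in the two earlier Cordella studies. The cohorts also differ in calendar period, European sites, treatment guidelines and some eligibility criteria.

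What does not stand is that the Kaplan-Meier plots cover the gap. They are indexed under the primary safety endpoints. SAP section 8 mentions Kaplan-Meier curves for time-to-event safety outcomes, but the index lists none for AEs or SAEs.

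**Conclusion.** The concern holds for the main analysis, for AE and SAE summaries and for the secondary sensor-failure rate. For events spread over time, equal hazards can yield cohort differences of about 20 to 30 points for a common event under even accrual, and roughly a doubling for sensor failure at the planning rate (6 to 9% against 3 to 4%). This rests on constant hazards and on follow-up inferred from dates. The documents give no cut-off date, site-level switch date or accrual curve, so a follow-up ratio above two is likely but not established.

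The primary safety endpoints and implant-period events are essentially unaffected, and the final analysis reduces the ratio to about 1.0 to 1.3 before attrition. The SAP already adjusts efficacy for exposure through the Poisson offset in section 7.1.1. The AE summaries have no counterpart.

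**What to change.** In SAP 8.2 and 8.3.4:

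- Report follow-up time (total patient-years, mean or median, range) by cohort and overall.
- Add events per 100 patient-years to the AE, SAE, DSRC and sensor-failure summaries, and/or Kaplan-Meier time-to-first-event estimates at 6 and 12 months, censored at last follow-up.
- Give the secondary sensor-failure rate a person-time or Kaplan-Meier denominator, and correct the sentence in 8.2 so that it covers all three endpoints.
- Keep the to-cut-off tables, which the whole-study endpoints need.
- Offer any days 0 to 180 by-cohort table as an addition. The AE tables use the ITT population, and subjects whose implant was not attempted (SAP 4.2) or not completed (Protocol 8.3.2) are followed for only 30 days. Such a table must state how it counts them.

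The cost is a little programming from dates already held, and some extra table columns. No new data are needed.
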